14.4 Analysis of Secondary Endpoints

General linear models and nonparametric approaches will be used to analyze the continuous outcomes of weight loss; dyspnea AUC at 24, 48, and 72 hours, length of hospital stay, and changes in biomarkers. Analysis of the additional safety and efficacy endpoints will emphasize comparisons among the treatment groups defined by the randomization.

14.5 Subgroup Analyses

Further analyses will be conducted to determine whether the effect of furosemide dose or mode of administration is modified by each of the following covariates:

- Admission blood pressure
- Baseline creatinine ($\leq 1.6 \text{ v.} > 1.6 \text{ mg/dL}$)
- Age (≤ 70 v. > 70)

Estimation of subgroup effects will be conducted within the linear models framework. To provide a conservative framework for the interaction testing, we will consider the interaction terms to be statistically significant if p<0.001.

15. DATA MANAGEMENT PROCEDURES

The DOSE-AHF trial is a prospective, randomized, controlled study where data will be collected, analyzed, and interpreted by the Duke Clinical Research Institute which functions as the DCC for the NIH Heart Failure Clinical Research Network. Data other than safety data cannot be used for publication or reporting outside of this study until the study is completed or discontinued by the DSMB or Heart Failure Clinical Research Network. This is necessary since dissemination of preliminary information may inappropriately affect the objectivity of this study. For this reason Study Investigators or other parties will not be allowed to perform subset analyses at any point before the conclusion of this study.

All prospective publications or presentations must be reviewed and approved by the HF Network steering committee and DCC representatives.

16. STUDY ADMINISTRATION

16.1 DSMB

A DSMB will be appointed by the NHLBI. This will be a group of individuals with pertinent expertise in heart failure and clinical trials. The DSMB will advise the sponsor regarding the continuing safety of current participants and those yet to be recruited, as well as the continuing validity and scientific merit of the trial.

16.1.1 Statistical Monitoring Plan

Interim data analysis for efficacy will not be conducted due to relatively small size and short duration of this phase II clinical trial. Safety data will be periodically assessed by the DSMB based on reporting of adverse events. There will be a planned assessment by the DSMB after 50 patients have been enrolled to evaluate compliance with the assigned treatment strategy (i.e., crossover). This will serve to allow reassessment of the planned sample size if needed.

16.2 Data Coordinating Center (DCC)

The Duke Clinical Research Institute will function as the DCC for this trial as specified by the sponsor (NIH Heart Failure Clinical Research Network grant).

16.3 Core Laboratories

This study will utilize a biomarkers core laboratory designated by the NHLBI and the DCC. Plasma specimens at baseline, 72 hours, day 7 (or discharge if earlier) and 60 days will be processed according to the procedures provided by the core laboratory and sent to the core laboratory on dry ice. Planned analyses include:

- Natriuretic peptides (BNP)
- Neurohormonal activation (Endothelin-1)
- Renal function (Cystatin C)
- Myocardial necrosis (Troponin T)

- Measures of collagen turnover/fibrosis (pro-collagen III NTP)
- Uric acid

18. APPENDICES

	Baseline	6, 12	24 hours	48 hours	72	96 hours	Day 7 or	60 days
		hours			hours		discharge	
Informed Consent	Х							
History and physical	Х		X	X	X	X	X	Х
CV Medication History	Х		X	Х	X	X	X	Х
Vital Signs	Х		X	X	X	X	Х	Х
Oxygen saturation	X		Х	X	X	X	Х	Х
Body weight	X		X	X	X	Х	X	X
VAS for PGA	X	Х	X	X	X	Х		
VAS for Dyspnea	Х	Х	X	X	X	X		
Fluid balance/24			X	X	X	X		
hours								
Cr, BUN, electrolytes	X		X	Х	X	Х	X	X
Plasma collection for	Х				X		X	Х
Biomarkers								
Adverse events			Х	X	X	X	Х	Х

18.1 Appendix A. Schedule of Assessments

18.2 Appendix B. List of Abbreviations

Abbreviation ACE ADHF AHF AICDs AUC BNP CO CRP CO CRP CRS DOSE ED EF JVP LVEDP LVEF IV IVRS KIM NIV NYHA PGA PAC PCWP	Definition angiotensin-converting enzyme acute decompensated heart failure acute heart failure automatic implantable cardioverter-defibrillators area under the curve B-type natriuretic peptide cardiovascular flow C-reactive protein Cardio-renal syndrome Diuretic Optimization Strategies Evaluation Emergency Department ejection fraction Jugular venous pressure left ventricular end diastolic pressure left ventricular ejection fraction Intravenous Interactive voice response system Kidney injury marker noninvasive positive pressure ventilation New York Heart Association Patient global assessment pulmonary artery catheter Pulmonary capillary wedge pressure
PCWP	Pulmonary capillary wedge pressure
SVR US	systemic vascular resistance United States
VAS	visual analogue scale

Site Number:		Patient Number:			
Assessment Date:	_(day)/	(month)	(year)	Time: _	_:

Appendix C. VAS Instruments 18.3

VAS – Global Well Being (PGA) Please draw a line on the scale to show how you feel right now. The number "0" equals the worst your have ever felt and the number "100" equals the best you have ever felt.

100 = Best you have ever felt

0 = Worst you have ever felt

Site Number:	Patient Num	Patient Number:		
Assessment Date: (day)/	(month)	(year)	Time:::	

VAS - Dyspnea

Please draw a line on the scale to show how your breathing feels right now. The number "0" equals the worst your breathing has ever felt and the number "100" equals the best your breathing has ever felt.

100 = I am not breathless at all

= I am as breathless as I have ever been

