11. OUTCOME DETERMINATIONS

11.1 **Primary Endpoints**

This study will use co-primary endpoints

• Change in serum creatinine from randomization to 72 hours

• Area under the Curve (AUC) for Patient Global Assessment by VAS over 72 hours

Rationale for Primary Endpoints:

Change in creatinine from randomization to 72 hours was chosen as the primary safety endpoint due to the observed association between diuretic dosage and worsening renal function and the known association of worsening renal function with other adverse outcomes.

For the assessment of short term efficacy, a variety of endpoints have been utilized in prior AHF studies. These include patient self assessments of symptoms, typically either dyspnea or global well being (termed patient global assessment (PGA)). These self assessments are usually performed using a visual analog scale (VAS) or Likert scale. The DOSE-AHF study will use the PGA by VAS over 72 hours as the primary endpoint for efficacy. The rationale for this choice is that although dyspnea is the primary symptom for most patients with AHF, other symptoms (fatigue, edema, etc) may also be important and should be captured in the primary efficacy endpoint. We have chosen a patient symptom assessment r ather than other measures of diuretic efficacy such as weight change or urine output, because while these measures capture the pharmacodynamic effects of diuretic therapy, they may not be tightly correlated with other clinical events (such as rehospitalization or death), and are therefore not ideal surrogates in the assessment of efficacy.

Patients will be asked to self assess both their general well being and their level of dyspnea using a visual analog scale (VAS) method. For PGA, patients will mark their global well being on a 10 cm vertical line, with the top labeled "best you have ever felt" and the bottom labeled "worst you have ever felt". For dyspnea, the labels will be "I am not breathless at all" and "I am as breathless I have ever been". The VAS is scored from 0 to 100 but the patient is unaware of the numerical value of their response. Patients will self assess both PGA and dyspnea at randomization, 6, 12, 24, 48, 72, and 96 hours. The area under the curve for PGA assessment over the first 72 hours will be the primary efficacy endpoint (AUC for PGA VAS).

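### The dyspnea VAS form words its upper anchor in two ways, which may add some noise to the secondary dyspnea AUC endpoints

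*Protocol*

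**What the plan says.** The dyspnea form in Appendix C (18.3) describes its scale twice.

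- **Instruction above the line:** 0 "equals the worst your breathing has ever felt" and 100 "equals the best your breathing has ever felt".
- **Labels on the line:** the top reads "100 = I am not breathless at all" and the bottom "I am as breathless as I have ever been". The number beside the lower label is lost in the text at hand. I take it to be 0, as in the instruction, and make nothing of its absence.

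Protocol section 11.1 gives the dyspnea labels as "I am not breathless at all" and "I am as breathless I have ever been". Apart from one dropped word these match the printed labels. That section does not mention the instruction sentence. On scoring it says: "The VAS is scored from 0 to 100 but the patient is unaware of the numerical value of their response".

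Dyspnea VAS AUC over 24, 48 and 72 hours is listed as a secondary endpoint (executive summary, sections 2.3 and 11.2). The form is completed at randomization and at 6, 12, 24, 48, 72 and 96 hours.

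**The concern.** The instruction anchors the top of the scale to the patient's own past. The label anchors it to the absence of a symptom. Someone who marks the line by one anchor may give a different score from someone with identical breathing who marks it by the other.

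This is plausible in the population enrolled. Section 6.1 requires a prior diagnosis of heart failure, at least one month of daily oral loop diuretic, and a daily dose of 80 to 240 mg furosemide or equivalent. For such patients, having no breathlessness at this moment and having the best breathing of one's life can be different states. The conflict lies at the upper end, towards which patients move as they improve.

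At stake is the precision of the dyspnea AUC comparisons, and whether a score near 100 has one meaning. A patient could also change reading from one assessment to the next.

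**Working it through.** **Step 1: compare the anchors.**

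| Source | Upper end | Lower end |
|---|---|---|
| Dyspnea form, instruction | best ever (relative) | worst ever (relative) |
| Dyspnea form, labels | no breathlessness (absolute) | most breathless ever (relative) |
| Section 11.1, labels | no breathlessness (absolute) | most breathless ever (relative) |
| PGA form, instruction and labels | best ever (relative) | worst ever (relative) |

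The lower ends of the dyspnea form mean nearly the same thing. The upper ends differ in kind. The PGA form shows no such split: its instruction and labels agree with each other and with section 11.1. The dyspnea instruction follows the sentence pattern of the PGA instruction, while the dyspnea labels use a different concept.

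**Step 2: direction.** It is not fixed.

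- A patient with no breathlessness now who remembers better breathing scores 100 by the label and less by the instruction.
- A patient who has always been somewhat breathless and is now at their best scores 100 by the instruction and less by the label.
- For many patients the two readings coincide.

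**Step 3: can the effect be sized?** Not from the documents. They give no SD, target difference or power for dyspnea AUC, and no information on how patients read the form. What follows is an illustration on assumed inputs only.

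Borrowed from section 14.3.2 (PGA, not dyspnea): SD 1500, difference 600, 150 v 150. Assumed: half the patients follow each anchor, and their scores differ by d points on average over 72 hours.

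- Formula check on the plan's PGA figure at two-sided 2.5%: Phi(600/(1500 × sqrt(2/150)) − 2.241) = Phi(3.464 − 2.241) = 88.9%, against 88% stated.
- Added SD = d × sqrt(0.5 × 0.5) × 72, combined in quadrature with 1500. The sign of d does not matter.
- For a secondary endpoint the general 5% level of section 14.1 applies, so the critical value is 1.960. The 2.5% level in section 14.3 is there for the two co-primary endpoints.

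| Assumed d | Added SD | Total SD | Power at 5% |
|---|---|---|---|
| 0 | 0 | 1500 | 93.4% |
| 10 | 360 | 1543 | 92.0% |
| 15 | 540 | 1594 | 90.3% |
| 20 | 720 | 1664 | 87.8% |

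**Step 4: how extreme is d = 20?** The bottom anchors nearly agree, so the gap should shrink towards the bottom of the line. If it shrinks in proportion to the score, a gap g at the top gives an average d = g × mean/100. With an assumed mean score of 50 to 60, d = 20 needs g = 20 × 100/60 = 33 up to 20 × 100/50 = 40 points at the top. Nothing in the protocol supports a gap of that size. A smaller d or a more uneven split costs less power.

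**The case against.** The strongest reply is that this is one line with one orientation and one 0-100 score. Both descriptions put good breathing at the top and bad breathing at the bottom, and the labels sit on the line the patient marks. The documents show a single form and a single schedule for everyone. Nothing in them shows that patients would split between the two readings. All of this stands, and it limits the point to a wording inconsistency.

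A reader might infer more in four ways. The documents support none of them.

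- **That the form contradicts section 11.1.** That section fixes the labels, and the printed labels follow it. It is silent on the instruction, so the mismatch lies within the form, between a sentence and its label.
- **That the dyspnea AUC mixes two scales.** There is one scale with one ambiguously described end. At most, some patients place themselves on it differently.
- **That the arms could differ systematically.** Allocation is randomized and both factors are double-blind with a double dummy (sections 7.1.1, 9.1 and 12.2). Any difference in reading is therefore expected to fall alike on all arms.
- **That a definite loss of power follows.** The split and every value of d above are invented, and the SD and target difference belong to PGA. Quoting the loss at 2.5% would also use a level set for the co-primary endpoints.

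What survives the reply is that the patient is given two non-equivalent definitions of 100 on one page, for no benefit.

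**Conclusion.** The inconsistency is real and minor. It can be read off a single page and does not depend on any text lost in extraction. Its possible consequence is undirected between-patient noise, and perhaps some within-patient noise, in the secondary dyspnea VAS AUC endpoints.

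Its size is unknown. The illustration suggests modest losses even under a generous assumption (about 93% to about 88% power at d = 20), but that range rests wholly on borrowed and assumed inputs and should not be cited as an estimate. Neither co-primary endpoint is affected: PGA AUC uses a form whose wording is consistent, and creatinine does not involve the VAS. No stated sample size, power or alpha changes.

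**What to change.** Before enrolment, reword the instruction sentence on the dyspnea form so that it uses the anchors already printed on the line and given in section 11.1: 0 for "I am as breathless as I have ever been" and 100 for "I am not breathless at all". The lower end needs little change in meaning, but taking both anchors from the labels leaves one definition of the scale. Restore the dropped word in section 11.1 at the same time.

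The cost is one sentence on a one-page form, with no added visits, data or patients. The downside arises if enrolment has begun, because a change would then put two form versions into the trial. Recording the version identifies the affected readings but does not make them comparable. In that case either record the version used at each assessment, or keep the current form throughout and note the ambiguity when the dyspnea results are reported.
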